6.3.1.1 Dose interruption due to liver signals

Eltrombopag dose must be interrupted when clinically indicated. The dose modifications for isolated ALT or AST elevation are listed in [Table 6-7](#). If the dose modification is based on local laboratory, then local laboratory results must be entered in the CRF.

Table 6-7 Criteria for eltrombopag dose adjustment based on liver enzyme and bilirubin levels

Dose modifications for ETB115	
Worst toxicity CTCAE ^a Grade (value) during the treatment	
Investigations (Hepatic)	
Isolated Total Bilirubin elevation	
> ULN – 1.5 x ULN	Maintain dose level
> 1.5 - 3.0 x ULN*	Interrupt dosing and weekly monitor LFTs ^b , or more frequently if clinically indicated, until resolved to $\leq 1.5 \times$ ULN: If resolved in ≤ 14 days, then resume at same dose level If resolved in > 14 days, then decrease one dose level ^e
> 3.0 - 10.0 x ULN**	Mandatory: Interrupt dosing and weekly monitor LFTs ^b , or more frequently if clinically indicated, until resolved to $\leq 1.5 \times$ ULN: If resolved in ≤ 14 days, then decrease one dose level ^e If resolved in > 14 days, then discontinue patient from study drug treatment. LFTs ^b will continue to be monitored weekly, or more frequently if clinically indicated, until total bilirubin have resolved to baseline or stabilization over 4 weeks.
> 10.0 x ULN**	Mandatory: Discontinue patient from study drug treatment The subject should be monitored weekly (including LFTs ^b), or more frequently if clinically indicated, until total bilirubin have resolved to baseline or stabilization over 4 weeks.
* Note: If total bilirubin $> 1.5 - \leq 3 \times$ ULN is due to the indirect (non-conjugated) component only, no changes to dose are required. ** Note: If total bilirubin $> 3.0 \times$ ULN is due to the indirect (non-conjugated) component only, and hemolysis as the etiology has been ruled out as per institutional guidelines (e.g., review of peripheral blood smear and haptoglobin determination), then decrease 1 dose level ^e and continue treatment at the discretion of the investigator	
Isolated AST or ALT elevation	
> ULN - 3.0 x ULN	Maintain dose level
> 3.0 - 5.0 x ULN	Maintain dose level. Repeat LFTs ^b as soon as possible, preferably within 48-72 hours from awareness of the abnormal results. If abnormal lab values are confirmed upon the repeat test, then monitor LFTs ^b weekly, or more frequently if clinically indicated, until resolved to $\leq 3.0 \times$ ULN Discontinue patient from the study treatment if elevation is combined with any of the following: 
• Clinical symptoms of liver injury or evidence for hepatic decompensation• Progressively increasing LFTs^b upon repeat testing• Persistence for ≥ 4 weeks
> 5.0 - 10.0 x ULN	Mandatory: Interrupt dose. Repeat LFTs ^b as soon as possible; preferably within 48-72 hours from awareness of the abnormal results. Monitor LFTs ^b weekly, or more frequently if clinically indicated until resolved to $\leq 3.0 \times$ ULN then:

Dose modifications for ETB115	
> 10.0 - 20.0 x ULN	If resolved in \leq 14 days, maintain dose level If resolved $>$ 14 days, decrease one dose level ^e Mandatory: Interrupt dose. Repeat LFTs ^b as soon as possible, preferably within 48-72 hours from awareness of the abnormal results. Monitor LFTs ^b weekly, or more frequently if clinically indicated until resolved to \leq baseline. Then decrease one dose level ^e .
> 20.0 x ULN	Mandatory: Discontinue patient from study drug treatment. Repeat LFTs ^b as soon as possible, preferably within 48-72 hours from awareness of the abnormal results. Monitor LFTs ^b weekly, or more frequently if clinically indicated until resolved to \leq baseline or stabilization over 4 weeks.
Combined^c elevations of AST or ALT and total bilirubin	
For patients with normal baseline ALT and AST and total bilirubin value, [AST or ALT $>$ 3.0 \times ULN] combined with [total bilirubin $>$ 2.0 \times ULN] without evidence of cholestasis ^d OR For patients with elevated baseline AST or ALT [AST or ALT $>$ 3 \times baseline] OR [AST or ALT $>$ 5.0 \times ULN], whichever is lower, combined with [total bilirubin $>$ 2 \times baseline AND $>$ 2.0 \times ULN]	Mandatory: Permanently discontinue patient from study drug treatment. Repeat as soon as possible, preferably within 48 hours from awareness of the abnormal results, then with weekly monitoring of LFTs ^b , or more frequently if clinically indicated, until AST, ALT, or bilirubin have resolved to baseline or stabilization over 4 weeks.

All dose modifications should be based on the worst preceding toxicity.
 
^a Common Toxicity Criteria for Adverse Events (CTCAE Version 4.03)
 
^b Core LFTs consist of ALT, AST, GGT, total bilirubin (fractionated [direct and indirect], if total bilirubin $>$ 2.0 \times ULN), and alkaline phosphatase (fractionated [quantification of isoforms], if alkaline phosphatase $>$ 2.0 \times ULN.)
 
^c "Combined" defined as total bilirubin increase to the defined threshold concurrently with ALT/AST increase to the defined threshold
 
If combined elevations of AST or ALT and total bilirubin do not meet the defined thresholds, please follow the instructions for isolated elevation of total bilirubin and isolated elevation of AST/ALT, and take a conservative action based on the degree of the elevations (e.g. discontinue treatment at the situation when omit dose is needed for one parameter and discontinue treatment is required for another parameter). After all elevations resolve to the defined thresholds that allow treatment re-initiation, re-start the treatment either at the same dose or at one dose lower if criterion for dose reduction is met.
 
^d "Cholestasis" defined as ALP elevation ($>$2.0 xULN and R value $<$2) in patients without bone metastasis, or elevation of ALP liver fraction in patients with bone metastasis. The R value is calculated by dividing the ALT by the ALP, using multiples of the ULN for both values. It denotes whether the relative pattern of ALT and/or ALP elevation is due to cholestatic (R \leq 2), hepatocellular (R \geq 5), or mixed (R $>$2 and $<$ 5) liver injury.
 
^e "One dose level" defined as eltrombopag dose reduction by 25 mg.
	

Eltrombopag can cause hepatobiliary laboratory abnormalities, severe hepatotoxicity, and potentially fatal liver injury. Serum ALT, AST and bilirubin should be measured prior to initiation of eltrombopag, every 2 weeks during the dose adjustment phase and monthly after establishment of a stable dose. Abnormal serum liver tests should be evaluated with repeat testing as described in [Table 6-7](#). If the abnormalities are confirmed, serum liver tests should be monitored weekly until the abnormalities resolve, stabilize, or return to baseline levels.

Both eltrombopag and cyclosporine can cause liver enzyme elevations. In the event that it is impossible to separate the effects of eltrombopag from the effects of cyclosporine, in order to protect patient safety, both drugs must be adjusted or interrupted until the liver normalizes, regardless of which drug may be responsible.

In the case of clinically significant elevated liver enzymes and/or bilirubin levels, a blood sample for the determination of cyclosporine blood concentrations must be collected, as per cyclosporine label. Cyclosporine dose must be decreased by 25% to 50% depending on cyclosporine blood concentrations and to control adverse events, including clinically significant lab abnormalities, in accordance with guidance provided in the cyclosporine label.

Discontinuation of cyclosporine must be considered if liver enzymes and/or bilirubin levels do not normalize within 4 weeks after dose modification or after two sequential dose decreases.

6.3.1.2 Dose modification for other reasons

Study drug dosing must be temporarily discontinued in patients unable to ingest the drug due to mucositis or vomiting.

Early discontinuation of eltrombopag

Eltrombopag must be permanently discontinued if any of the following events occur or is identified at any time during the study:

- Cytogenetic abnormalities associated with dysplastic bone marrow findings
 - a. Monosomy 7 – discontinue eltrombopag
 - b. Other cytogenetic abnormalities not associated with worsening blood counts or bone marrow dysplastic findings – discontinuation at physician and/or Investigator discretion. A more frequent bone marrow aspirate monitoring of cytogenetic abnormalities and dysplastic findings may be performed in this patient group.
- Thromboembolism considered related to drug occurs
- Development of MDS or AML
- Patient receives HSCT
- Positive pregnancy test, at any time during the study
- Difficulties to continue the study treatment due to AE(s)
- Patient is found to be significantly non-compliant with the requirements of the protocol (including treatment noncompliance)

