>400 000/ μ L (untransfused) at any time on study	Discontinue eltrombopag for one week. If platelet count falls to <200 000/ μ L restart eltrombopag at a dosage decrease of 25 mg/day

A decrease in eltrombopag exposure was observed with co-administration of 200 mg and 600 mg cyclosporine. This decrease in exposure is not considered clinically meaningful. The prescribing information for eltrombopag recommends monitoring platelet count at least weekly for 2 to 3 weeks when eltrombopag is co-administered with cyclosporine. Therefore, in this study platelet count must be monitored weekly from day 1 to 2 month and every 2 weeks from 2 to 6 months.

In case of early discontinuation of eltrombopag, cyclosporine should be continued until 6 months for all patients and for responders who do not relapse prior to 6 months tapering to 24 months, following the cyclosporine dosing guidelines.

Table 6-3 Eltrombopag Dosages and Available Treatment Formulations

Study Treatment	Pharmaceutical Form and Route of Administration	Strength	Frequency and/or Regimen
ETB115/eltrombopag	Tablet for oral use	12.5 mg	Once daily
ETB115/eltrombopag	Tablet for oral use	25 mg	Once daily
ETB115/eltrombopag	Tablet for oral use	50 mg	Once daily
ETB115/eltrombopag	Tablet for oral use	75 mg	Once daily

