Cyclosporine dose may be interrupted temporarily or discontinued early when clinically indicated at the discretion of the investigator or treating physician according to the local cyclosporine prescribing information. The parenteral route of administration may be used temporarily for cyclosporine administration if indicated. Temporary interruptions for transient toxicities or dose adjustments will be reported. In case of early discontinuation of cyclosporine, eltrombopag should be continued until 6 months, following the eltrombopag dosing guidelines.

Table 6-6 Cyclosporine Dosages and Available Treatment Formulations*

Study treatments	Pharmaceutical form and route of administration	Strengths	Frequency and/or Regimen
Cyclosporine	Soft gelatin capsule	10 mg	Every 12 hours
Cyclosporine	Soft gelatin capsule	25 mg	Every 12 hours
Cyclosporine	Soft gelatin capsule	50 mg	Every 12 hours
Cyclosporine	Soft gelatin capsule	100 mg	Every 12 hours

*Treatment formulation availabilities depend on countries marketing authorization as a local commercial supply is used.

Cyclosporine dose management can be rounded to the nearest quartile (25 mg increments), e.g. : 'If a patient weighs 82 kg, the total CsA dose will be 820 mg which would result in 410 mg every 12 hours. The q12 dosing can be rounded to 400 mg. Furthermore, if a patient weighs 67

kg, the total daily dose will be 670 mg which would result in 335 mg every 12 hours. The q12 dosing for this patient can be rounded to 325 mg every 12 hours.”

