7.1.5 Discontinuation of study treatment

Patients may voluntarily discontinue from the study treatment (eltrombopag and/or cyclosporine) for any reason at any time. If a patient decides to discontinue from the study or fail to return, the investigator should make a reasonable effort (e.g. telephone, e-mail, letter) to understand the primary reason for this decision and record this information in the patient's chart and on the appropriate eCRF pages, see [section 7.1.8](#). They may be considered withdrawn if they state an intention to withdraw, fail to return for visits, or become lost to follow-up for any other reason.

The investigator may discontinue eltrombopag and/or cyclosporine for a given patient if he/she believes that continuation would be detrimental to the patient's well-being.

Patients who discontinue eltrombopag before 6 months, should continue cyclosporine treatment until 6 months (all patients) and until 24 months (responders only).

Patients who discontinue cyclosporine before 6 months, should continue eltrombopag treatment until 6 months.

Patients who discontinue both eltrombopag and cyclosporine before 6 months or discontinue cyclosporine during the additional 18 months follow-up (responders only) should be scheduled for an end of study treatment visit as soon as possible after the last dose of study treatment

(eltrombopag and cyclosporine), at which time all the assessments listed in the visit evaluation schedule (under EOT) will be performed ([Table 7-2](#)). At a minimum, all patients who discontinue eltrombopag and/or cyclosporine (premature discontinuation, with patients no longer being in the study), including those who refuse to return for a final visit, will be contacted for safety evaluations during the 30 days following the last dose of study treatment.

The investigator must also contact the IRT to register the patient's discontinuation from study treatment.

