7.2.2.5.4 Pregnancy and assessments of fertility

Females of child-bearing potential are defined as all females physiologically capable of becoming pregnant. This includes female children and adolescents who are post-menarche or who experience menarche during the study. Pregnancy test will be performed for all females of child-bearing potential at baseline according to the schedule in [Table 7-1](#) and [Table 7-2](#).

Serum pregnancy test is required at screening and monthly until the end of treatment of eltrombopag and cyclosporine or the end of the study (depending upon the reason why the patient discontinued study medication). During the additional 18 months follow-up (responders only) of the study, it is highly recommended to perform the pregnancy test on monthly basis but the SOC can be also followed at the discretion of the investigator practice. Urine or serum pregnancy testing will be repeated approximately every 4 weeks while receiving study drug until study drug discontinuation. A serum pregnancy test may be used to confirm the results of a urine pregnancy test. Additional pregnancy tests may be performed at the investigator's discretion during the study. Additional pregnancy tests may be performed at the investigator's discretion during the study. Patients becoming pregnant must be discontinued from study drug.

Females of child-bearing potential who are or might become sexually active, must be informed of the potential teratogenic risk with eltrombopag and cyclosporine and the need for highly effective contraception to prevent pregnancy while on eltrombopag and cyclosporine therapy:

Use of oral, injected or implanted hormonal methods of contraception or placement of an intrauterine device (IUD) or intrauterine system (IUS) or other forms of hormonal contraception that have comparable efficacy (failure rate < 1%), for example hormone vaginal ring or transdermal hormone contraception.

Contraception must be used during the study and for 3 months after stopping treatment. The decision on the contraceptive method should be reviewed at least every 3 months to evaluate the individual need and compatibility of the method chosen.

Sexually active male patients, if they don't agree to abstinence, must use agree to use of highly effective methods of contraception as outlined in the Inclusion Criteria while taking study drugs and for 3 months after stopping treatment, and should not father a child during this period.

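### A positive pregnancy test before month 6 stops only eltrombopag in 6.3.1.2, out of step with 7.2.2.5.4; the 24-hour pregnancy report also stops short of the 3-month contraception window

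*Protocol*

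**What the plan says.** **Stopping treatment**

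- Protocol 6.3.1.2, in its part on early discontinuation of eltrombopag, opens its list with "Eltrombopag must be permanently discontinued if any of the following events occur or is identified at any time during the study". One entry is "Positive pregnancy test, at any time during the study". Cyclosporine is not mentioned in that entry.
- Protocol 6.1.1.1: "In case of early discontinuation of eltrombopag, cyclosporine should be continued until 6 months for all patients". The same sentence continues the drug with tapering to 24 months for responders who have not relapsed, and makes continuation subject to the cyclosporine dosing guidance.
- Protocol 7.1.5 repeats the rule: month 6 for everyone, month 24 for responders. Neither section exempts pregnancy.
- Protocol 7.2.2.5.4: "Patients becoming pregnant must be discontinued from study drug". Its next paragraph says that women of child-bearing potential "must be informed of the potential teratogenic risk with eltrombopag and cyclosporine".
- Two passages give discretion. In 6.1.1.2: "Cyclosporine dose may be interrupted temporarily or discontinued early when clinically indicated at the discretion of the investigator". In 7.1.5: "The investigator may discontinue eltrombopag and/or cyclosporine for a given patient if he/she believes that continuation would be detrimental".

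**Reporting and follow-up**

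- Protocol 8.4 makes a 24-hour report mandatory for a pregnancy occurring while the patient is on study treatment. Its second paragraph asks that pregnancies be recorded on the pregnancy form and reported, with no deadline.
- Protocol 7.2.2.5.4 requires contraception for 3 months after treatment stops.
- Table 7-2, which covers responders only, provides pregnancy tests up to 2 months after cyclosporine stops. Home urine tests are allowed, but only blood results go into the eCRF.

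**The concern.** A site that gets a positive test before month 6 is likely to open the list of reasons to stop eltrombopag. That list settles eltrombopag and is silent on cyclosporine. The next general rule, in 6.1.1.1 or 7.1.5, says to carry on with cyclosporine. The instruction that should govern is in the laboratory-assessment part of the protocol, and its sentence does not name the drugs. The decision concerns fetal safety, so a site should not have to reconcile four sections to reach the right action.

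After the last dose, the protocol treats the next 3 months as a period in which pregnancy should be avoided. It does not attach its prompt-report duty to that period. In a responder, a test that the protocol itself provides could turn positive without triggering the 24-hour rule.

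**Working it through.** **Part 1: which instruction applies to cyclosporine.** No arithmetic applies here; the check is a comparison of the text.

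| Place (Protocol) | Eltrombopag | Cyclosporine | Force |
|---|---|---|---|
| 6.3.1.2 | stop permanently | not mentioned | must |
| 6.1.1.1 | already stopped early | continue, within dosing guidance | should |
| 7.1.5 | already stopped early | continue | should |
| 7.2.2.5.4 | stop | stop, if study drug means both | must |

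The last row turns on what study drug means.

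- *For both drugs.* The paragraph that holds the stop rule sets monthly tests to the end of eltrombopag and cyclosporine treatment and covers the 18-month follow-up. It then asks for tests about every 4 weeks for as long as study drug is taken. Only cyclosporine is given in that follow-up, so the term must include it. Protocol 6.1 names both drugs as study treatments. SAP 2.1.3 defines study drugs as either one.
- *For eltrombopag alone.* Protocol 6.1.1.1 uses the term once with eltrombopag in brackets, in a section about eltrombopag. If this meaning were carried into 7.2.2.5.4, no pregnancy-specific rule would stop cyclosporine.

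The first reading is the better one. On it, 7.2.2.5.4 requires both drugs to stop, and the two defaults conflict with it when read alone.

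Two features make the omission easier to miss. Section 6.3.1 refers sites to 7.1.5.1 for events that force permanent discontinuation, but 7.1.5.1 is the replacement policy and lists none. Some other safety rules do say what happens to cyclosporine: 6.3.1.1 adjusts or interrupts both drugs when a liver signal cannot be attributed, and 6.3.3.1 lets a patient stay on cyclosporine after a thrombosis.

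The problem is confined to the first 6 months, because eltrombopag ends at month 6 and the defaults apply only after an early eltrombopag stop.

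**Part 2: days outside the mandatory 24-hour report.**

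Inputs: a month is 365.25 / 12 = 30.4375 days (SAP 2.1.3); contraception lasts 3 months after stopping (Protocol 7.2.2.5.4); on-treatment for the safety analysis runs to last dose + 30 days (Protocol 10.5.3.1).

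- Contraception window: 3 × 30.4375 = 91.3 days.
- Literal reading of 8.4 (coverage ends with the last dose): 91.3 − 0 = 91.3 days uncovered.
- Most generous reading (last dose + 30 days): 91.3 − 30 = 61.3 days uncovered.
- Table 7-2 tests, responders only: to 2 × 30.4375 = 60.9 days after cyclosporine stops. On the generous reading, 60.9 − 30 = 30.9 of the tested days still lie outside the 24-hour duty.

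The gap concerns female patients. For female partners of male patients, 8.4 asks for outcomes without limiting them to time on treatment.

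**The case against.** The strongest answer on part 1 is that the matter is already decided. One specific mandatory sentence in the pregnancy section outranks two general sentences that say should. The continuation sentence in 6.1.1.1 is itself conditional on the cyclosporine dosing guidance, and 6.1.1.2 brings in the contraindications in the local label and allows early stopping when clinically indicated. The 6.3.1.2 list is about eltrombopag, and its entries for transplant, MDS or AML, and non-compliance do not mention cyclosporine either. All of this stands. It makes the problem one of inconsistent text, but the two defaults still lack a pregnancy exception.

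On part 2, the second paragraph of 8.4 already asks for pregnancies to be recorded and reported. A pregnancy that began on treatment and is discovered later is covered, because the clock runs from learning of it. A congenital anomaly is an SAE (8.2.1) and stays reportable after 30 days if causality is suspected (8.2.2). Drug levels also fall well before 3 months. With the longest half-lives in 1.2.1.3.1 and 1.2.2.2, five half-lives are 5 × 35 h = 175 h, or 7.3 days, for eltrombopag (ITP patients) and 5 × 20.4 h = 102 h, or 4.3 days, for cyclosporine (severe liver disease). No half-life in SAA is given; assuming three times the eltrombopag value gives about 22 days. These points stand too. What is missing is only the mandatory prompt report.

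A reader might infer that the protocol directs pregnant patients to stay on cyclosporine, or might count the time left to month 6 or month 24 as fetal exposure. The documents support neither. The mandatory sentence governs, and the scheduled time left is not an expected exposure; for a responder it can exceed the length of any pregnancy.

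**Conclusion.** Part 1 holds as an internal inconsistency, at low severity. In the first 6 months, the stopping list omits cyclosporine and two general defaults continue it, against a specific mandatory rule that covers both drugs. This rests on reading study drug in 7.2.2.5.4 through its own paragraph and 6.1. A site would go wrong only by missing that section or by reading the term as eltrombopag alone. No exposure length should be attached to it.

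Part 2 holds as a secondary point. Between about 61 and 91 days of the required contraception window carry no mandatory 24-hour report for female patients. A reader might infer that such pregnancies go unreported or that late fetal exposure is likely; the documents show neither.

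The documents give no pregnancy rate, and few events would be expected among the 54 patients enrolled (SAP section 1). There is no effect on endpoints, analysis or sample size. Enrollment ended on 11-May-2020, so the part 1 period closed about November 2020. The last responders could take cyclosporine until about May 2022, so part 2 stayed relevant until about three months after that.

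**What to change.** **Part 1**

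- In 6.3.1.2 and in the 7.2.2.5.4 sentence, state that a positive pregnancy test permanently stops both eltrombopag and cyclosporine.
- In 6.1.1.1 and 7.1.5, exempt pregnancy from the text that continues cyclosporine after an early eltrombopag stop.

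**Part 2**

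- In 8.4, extend the 24-hour report to any pregnancy in a female patient up to 3 months after the last dose of either drug, including one found by a home urine test.
- At the 30-day safety follow-up, remind patients to contact the site if they become pregnant within that window.

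The cost is about one sentence in each of the five sections, using the existing pregnancy form. The downside is a few extra reports and one reminder. Patients who have left the study may still not call, so the extended duty would improve prompt reporting without guaranteeing it.
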